This Phase 2, open-label study of the investigational anti-angiogenesis agent axitinib, AG-013736. A 2-stage Simon Minimax design will be used with 18 treated patients in the first stage and 14 treated patients in the second stage. At least 1 patient must have a confirmed response (CR or PR) in the first stage in order to proceed to the second stage. At the end of the study, at least 4 confirmed responses in 32 treated patients must be observed in order to recommend further studies in this patient population.

For a total of up to 32 may be treated in order to gain additional safety and activity information should the trial be positive at the end of Stage 2.

Treatments:

Axitinib will be administered 5 mg orally twice each day (BID) continuously. Dose adjustments will be based on adverse events.

Protocol: 03/21/16

Endpoints:

Primary Endpoint(s):	Response rate according to RECIST criteria	
	A response will also be considered to have	
	occurred if there is a >/= 25% reduction in the	
	involved nodal basin specific uptake value (SUV)	
	on PET/CT (see Appendix C)	
Secondary Endpoints:	1) Progression-free survival (PFS)	
	2) Safety profile of AG-013736	
	3) Duration of response	
	4) Overall survival	

Page 5 of 53

Safety Measurement/Parameters:

Safety will be assessed by collecting adverse event information on each patient including results of physical examinations and laboratory testing.

Statistical Methods:

Demographic data will be displayed and summary statistics will be provided. The results of safety and efficacy evaluations will be tabulated and displayed.

The estimated response rate and its 95% confidence interval will be provided. The duration of response, progression-free survival, and survival will be summarized.

Study Schedule/Flowchart:

Study tests and procedures will include multiple examinations, laboratory tests, and radiographic procedures according to schedule of tests and procedures in the table below:

TABLE - SCHEDULE OF TESTS AND PROCEDURES

Protocol Activities	Screening	Study Treatme	ent					
	≤ 18 Days Prior to Enrollment	Day 1 to Day 56 (-3/+3)	Day 57 to Day 91 (-3/+3) Treatment Rest/ Pre-Op ^v	Surgery 14-21 Days Post Last Dose	Recovery 28 Days Post- Sugery ^w	Every 4 Weeks* Progression/Early Termination	Every 16 Weeks	Follow-up Day 28 After Last Dose ^x
Informed consent ^a	X							
Medical history ^b	X							
Concomitant treatment ^c	X	X				X		X
Physical exam ^d	X	X**	X		X	X		X
Weight, height, temperature ^e	X	X	X		X	X		X

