Blood pressure, pulse ^f	X	X	X		X	X		X
Home blood pressure monitoring ^g		Pa	rticipant Ins	structed to M	lonitor thi	oughout st	udy.	
ECOG performance statush	X	X	X		X	X		X
Hematology ⁱ	X	X**	X		X	X		X
Chemistry ^j	X	X**	X		X	X		X
Urinalysis ^k	X	X**	X		X	X		X
12-Lead electrocardiogram ¹	X		X		X			
Fecal Immuchemical Test m	X							
Tumor measurements ⁿ PET/CT	X		X		X (post surgery baseline		X	
Soluble protein samples ^o Marker of drug activity		X	X			X ^y	X	
Tumor genomics ^p		X		X From node dissection				
Blood genomic sample ^q		X						
Safety assessment (adverse events) ^s		X	X		X			
Survival ^t		Throughout the study period						
Serum or urine pregnancy test ^u Until at least one year after the initial dose for the last treated patient	X	X			X		X	X
Axitinib Treatment		X				X		
Treatment held preoperatively			X					
Lymph node dissection				X				

Notes to Table

Tests and procedures should be done on schedule, but occasional changes by +/- 4 days are allowable for holidays, vacations, and other administrative reasons.

- * Cycle length is 4 weeks [two cycles prior to surgery].
- ** Unnecessary to repeat before first dose if screening assessment was performed within 7 days prior to first dose.
- ^a Any time prior to any procedures performed solely for this study.
- b Including use of nicotine products.
- ^c Should be collected from screening to the follow-up period.
- d After the initial complete examination, targeted examinations based on signs and symptoms may be performed.
- Height need not be collected after the first measurement.
- Blood pressure and pulse to be measured with the patient in the seated position after the patient has been sitting quietly for 5 minutes.
- Patients receiving AG-013736 will receive blood pressure monitoring devices. Patients should take blood pressure at least once each day and should be recorded in a patient diary.
- ^h See Appendix D for performance status scale.
- Hgb, Hct, WBC with differential, and platelets. Prothrombin time and partial thromboplastin time should be done prior to the first dose and then as clinically indicated.
- Blood urea nitrogen (BUN), creatinine, sodium (Na⁺), potassium (K⁺), chloride (Cl⁻), bicarbonate (HCO₃⁻) or CO₂, alkaline phosphatase, lactate dehydrogenase (LDH), alanine aminotransferase (ALT, or SGPT), aspartate aminotransferase (AST, or SGOT), total protein, albumin, total bilirubin, and glucose.

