- Protein, glucose, and blood. If protein ≥2+ by semiquantitative method (eg, dipstick) then quantitate by 24-hour urine collection. Dose adjustment may be required. Screening urinalysis should include microscopic examination of the sediment.
- Additional ECGs as clinically indicated.
- ^m Subjects with a positive fecal immunochemical test (FIT) from blood test result should be evaluated for active gastrointestinal bleeding. Additional tests as clinically indicated.
- Tumors assessments by PET/CT will be performed every 8 weeks using RECIST criteria (see Appendix C). Response (CR/PR) requires confirmation at least 4 weeks after the response is noted. For patients who have not progressed after discontinuing study drug, additional tumor assessments should be performed approximately every 8 weeks until patient meets criteria for progression or alternate therapy started.
- ^o See Appendix F for collection, processing and shipping instructions. 10 ml of blood will be drawn for this sample.
- Optional for patients on Stage 1, required for patients entered on Stage 2 of the study. Second biopsy should be on Day 29 +/-4 days. A punch, core, or excisional biopsy should be used to obtain approximately 4 mm cube of tumor tissue. See Appendix G for processing and shipping instructions.
- Genomic analysis will be performed for each subject from a blood sample taken prior to dosing on Day 1. A 5 mL blood sample will be collected in a purple cap EDTA tube. Blood samples will be stored at -20°C until shipment on dry ice to the address given in the Study Manual. Appendix G has further details.
- Adverse events should be collected from the time of consent and throughout the study period until at least 28 days after the last dose of study drug and followed until resolution or stabilization.
- All patients should be followed for survival at least every 3 months after discontinuing study treatment until at least one year after the initial dose for the last treated patient.
- ^u Patient of childbearing potential must have a negative pregnancy test within 7 days prior to treatment and must be using appropriate birth control or practicing abstinence.
- ^v Minimum rest period is 14 days prior to surgery.
- Winimum rest period is 28 days post surgery; maximum rest period 56 days post surgery.
- Patients go off treatment after one year if they have not progressed.
- .y Done at first 4 week mark only.

TABLE OF CONTENTS

	PAGE
PROTOCOL SYNOPSIS	2

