3.5.8. Efficacy Assessments

All baseline lesion assessments should be performed as close as possible to but not more than 4 weeks before treatment. At baseline, tumor lesions will be categorized as target or nontarget. All patients will be evaluated for response according to RECIST (see Appendix C) and/or by PET/CT. Because resection of the involved nodal basin will occur within 3 to 4 weeks of initial therapy, no confirmatory scans will be done. All scans for tumor assessment must be performed at the same imaging site for consistency. Transfer of tumor assessment images will be done electronically whenever possible. The tumor assessments will be formally evaluated within 2 weeks of receipt by the vendor. As part of tumor assessments, exploratory studies of volumetric determinations of individual lesions and other methods of measuring tumor size may be performed.

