Initially, 18 patients with the indication and treated with AG-013736 will be evaluated for response (CR or PR). Once 1 or more confirmed responses are documented, the study will proceed to Stage 2. If 1 confirmed response has not been documented by the time 18 patients have been started on treatment, enrolment will be temporarily suspended to allow for treatment and evaluation of these patients.

6.1.1.2. Stage 2

In Stage 2, 14 additional patients will be enrolled and treated, to a total sample size of 32 treated patients. If 4 or more responses (CR or PR) are documented among these 32 patients, the indication will be recommended for further study.

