6.2. Methods of Analysis

The emphasis of the statistical analyses in this study will be on estimation. Due to the exploratory nature of this study, no imputation of missing data will be done.

An initial assessment will be done after 18 patients with eligible diagnoses have been treated. If there is at least 1 patient with a confirmed response, the trial will be expanded to a total of 32 treated patients with eligible diagnoses. The final analysis will be conducted when at least 1 of the following conditions is met:

- If 4 or more confirmed responses (CR or PR) are documented among the first 32 treated patients enrolled with eligible disease by the end of Stage 2 and the study is not expanded to add additional patients, the final analysis will take place once data have been compiled on all 32 treated patients through at least 1 year from the date of the first dose for the last patient enrolled. The final analysis will occur sooner if the study is discontinued due to lack of clinical response;
- If the study is expanded to derive further information on safety and activity to be used to aid in the design of additional studies with AG-013736 in this indication, then final analysis will take place once data have been compiled on all treated patients through at least 1 year from the date of the first dose for the last patient enrolled.
- The study is complete as defined in Section 3.6.

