6.2.1. Primary Efficacy Parameter

The primary efficacy parameter is the overall response rate. All patients who receive at least 1 dose of AG-013736 and have a baseline assessment of disease will be included in the analysis. Patients who were inadvertently enrolled (eg, patients who are determined to have the incorrect histological cancer type after receiving a dose of medication, based on their screening disease

Page 36 of 53

Protocol: 03/21/16

assessment) will be excluded from analyses and will be replaced. The overall response rate is defined to be the percentage of patients with a confirmed CR or PR. Patients who die, progress, or drop out for any reason after receiving a dose of AG-013736 prior to reaching a CR or PR will be included in the analysis as non-responders.

For response rate, duration of response, and progression-free survival, assessments from the independent third party will be considered the primary data. Additionally, the primary analyses for these endpoints will be based on the data collected from the disease assessment method(s) used starting at baseline to follow a patient's lesions. If PET scans or ultrasound is used on some patients during study who are believed to have central tumor necrosis or intratumor bleeding, these data and any subsequently collected lesion assessment data will not be used in the primary analyses but may be used in exploratory analyses of response rate, duration of response and progression-free survival.

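### The primary endpoint and both decision rules count confirmed responses, but the plan does no confirmatory scan before the nodes are resected; the single-scan definition it appears to intend must be written into the rules.

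*Combined protocol and SAP*

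**What the plan says.** **Confirmation required.**

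- Section 6.2.1, primary endpoint: "The overall response rate is defined to be the percentage of patients with a confirmed CR or PR".
- Synopsis, Study Design: "At least 1 patient must have a confirmed response (CR or PR) in the first stage in order to proceed to the second stage". The same paragraph asks for at least 4 confirmed responses in 32 treated patients.
- Section 6.1.1.1: "Once 1 or more confirmed responses are documented, the study will proceed to Stage 2". Section 6.2 repeats the gate in the same terms.
- Section 6.2, final analysis: "If 4 or more confirmed responses (CR or PR) are documented among the first 32 treated patients enrolled with eligible disease".
- Schedule of Tests and Procedures, tumor-measurement footnote: "Response (CR/PR) requires confirmation at least 4 weeks after the response is noted".

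**Confirmation not done, or response fixed at one assessment.**

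- Section 3.5.8: "Because resection of the involved nodal basin will occur within 3 to 4 weeks of initial therapy, no confirmatory scans will be done".
- The schedule has a single PET/CT entry between the start of treatment and surgery. The next, in the recovery column, is labelled "post surgery baseline".
- The synopsis primary objective limits response to the lead-in period. Section 3.1 has response determined by restaging PET/CT after two months of therapy.
- Appendix C makes the assignment of CR and PR as best response depend on meeting the measurement criteria and mentions no confirmation.

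Section 6.1.1 sets the null and target rates at 5% and 20% without saying whether they are confirmed or single-scan rates.

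**The concern.** The response count drives the decision to open Stage 2 and the recommendation for further study. An analyst who follows section 6 counts only confirmed responses. A site that follows section 3.5.8 and the schedule produces no scan that could confirm one before the nodes are removed. No passage says which instruction takes precedence.

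Section 3.5.8 describes procedures and does not change the endpoint definition in 6.2.1 or the decision rules. The opening of section 6 also says that major changes to the primary endpoint definition will be reflected in a protocol amendment, so quietly dropping the confirmation requirement at analysis would depart from the plan. The choice could then be made after the scans have been read, in a trial where one response opens Stage 2 and four decide the outcome.

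**Working it through.** **1. Reproduce the stated design.** Inputs from section 6.1.1: 18 patients then 14, null rate 5%, target rate 20%, alpha and beta 0.10. Stop at 0/18; recommend at 4 or more of 32. With X the Stage 1 count and Y the Stage 2 count:

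- P(stop at Stage 1) = (1 − p)^18
- P(recommend) = Σ over x = 1 to 18 of P(X = x) × P(Y ≥ 4 − x), with X ~ Bin(18, p) and Y ~ Bin(14, p)

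| Term | p = 0.05 | p = 0.20 |
|---|---|---|
| P(stop), X = 0 | 0.3972 | 0.0180 |
| X = 1 and Y ≥ 3 | 0.3763 × 0.0301 = 0.0113 | 0.0811 × 0.5519 = 0.0447 |
| X = 2 and Y ≥ 2 | 0.1683 × 0.1530 = 0.0258 | 0.1723 × 0.8021 = 0.1382 |
| X = 3 and Y ≥ 1 | 0.0473 × 0.5123 = 0.0242 | 0.2297 × 0.9560 = 0.2196 |
| X ≥ 4 | 0.0109 | 0.4990 |
| P(recommend), from unrounded terms | 0.0721 | 0.9015 |

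The plan states about 40%, 1.8%, and error rates below 0.10. All are reproduced: alpha is 0.0721 and beta is 1 − 0.9015 = 0.0985. The sample-size arithmetic is correct; the defect lies in what is counted.

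**2. Apply the confirmed definition to the planned assessments.** Confirmation needs a second assessment at least 4 weeks after the first. One pre-operative PET/CT is scheduled, 3.5.8 rules out a confirmatory scan, and the next scheduled scan is a new baseline after the basin has been removed. For response in the resected nodes the countable rate is therefore p = 0. Then P(stop at Stage 1) = 1^18 = 1 and P(recommend) = 0, whatever the drug does to those nodes.

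**3. Apply the single-scan definition.** The count is status at the pre-operative assessment against baseline. The figures in step 1 apply as they stand if 5% and 20% are rates on that scale.

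**4. How much the scale matters.** With the 0/18 and 4/32 rules fixed, P(recommend) reaches 0.10 at p = 5.61% and 0.90 at p = 19.94%, so there is little slack on either side. As an illustration, let c be the fraction of single-scan responses that would be confirmed. The documents give no value, so a range is shown.

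| Assumed c | Power if 20% is a single-scan rate but confirmed responses are counted (p = 0.20c) | Alpha if 5% is a confirmed rate but single-scan responses are counted (p = 0.05/c) |
|---|---|---|
| 0.9 | 0.846 | 0.097 |
| 0.8 | 0.768 | 0.134 |
| 0.5 | 0.393 | 0.393 |

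**The case against.** The best defence is that the intent is plain. Section 3.5.8 is the specific provision and gives its reason. The synopsis objective, section 3.1 and Appendix C point the same way, and the confirmation wording looks like general text left uncorrected. On that reading the stated design holds. This stands as evidence of intent, and it is why the fix adopts the single-scan definition. It does not cure the text: the endpoint definition and both decision rules still say the opposite.

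Some places that omit the word are also weak evidence of conflict. Section 6.2.1.1 sits under 6.2.1 and inherits its confirmed definition. The rule in 6.1.1.2 and the shorter gate in the synopsis can be read as shorthand. The point does not rest on them.

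A reader might infer two stronger things that the documents do not support.

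- **That the calendar makes confirmation impossible.** The surgery column reads "Surgery 14-21 Days Post Last Dose". With the last dose on Day 56, surgery falls on Day 70 to 77, which is 13 to 20 days after an assumed Day 57 scan. But the general window of plus or minus 4 days, applied to both, allows Day 53 to Day 81, which is 28 days. The schedule also gives the scan no exact day. The sound argument is that no second pre-operative scan is planned.
- **That lesions removed by surgery would be counted as drug responses.** The best-response sentence in Appendix C runs to progression or recurrence and does not itself close this off. The lead-in limit in the synopsis objective, section 3.1 and the post-surgery baseline label all run against it. It deserves one clarifying clause, not a probability.

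**Conclusion.** The concern holds as a conflict between two definitions of response, in text that governs the primary endpoint and both decisions. Under the confirmed definition the planned assessments cannot yield a countable response in the resected nodes, so the 1.8% and the beta below 0.10 are not delivered. Under the single-scan definition the design performs as stated (0.397 and 0.018 for early stopping, alpha 0.072, power 0.901).

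The first conclusion assumes that the schedule and 3.5.8 are followed and is limited to the resected nodes. It does not show that the trial must fail. The second assumes that 5% and 20% are single-assessment rates. The likely intent is single-scan, but the rules need to say so before the count is made.

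**What to change.** Amend the wording as follows.

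1. Remove the confirmation requirement from the endpoint and decision rules in the synopsis (Study Design) and sections 6.1.1.1, 6.2 and 6.2.1, and delete the confirmation sentence from the tumor-measurement footnote.
2. Define response, for the primary endpoint and both decision rules, as status at the end-of-lead-in pre-operative assessment against baseline, by the protocol's response criteria. Reconcile this with section 6.2.1, which keeps some PET data out of the primary analyses.
3. In Appendix C, limit best overall response to the lead-in phase for this endpoint, so that post-operative scans neither establish nor confirm a response.
4. State in section 6.1.1 that 5% and 20% are unconfirmed, single-assessment rates. If they were meant as confirmed rates, restate the operating characteristics on the scale actually counted.

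The cost is an amendment, with no added scans or patients if the rates are single-assessment rates. If they were confirmed rates, the cut-offs or sample size may have to change. The downside is that the result is an unconfirmed response rate and must be labelled so.

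The surgery-timing statements (the schedule, its notes and 3.5.8) and the SUV response thresholds (synopsis, 3.1 and Appendix C) also conflict. These are separate matters for the sponsor to reconcile; no timing or threshold is proposed here.

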3.5.9. Timing of Procedures

The minimum required prestudy, on study, and follow up evaluations are summarized in the Schedule of Tests and Procedures Table. Other parameters and/or increased frequency of examinations or clinical follow up may be needed depending on the findings during the study. Assessments should be performed on schedule, but a window of +/-4 days is permitted for holidays, vacations, and other administrative reasons.

3.5.9.1. Screening Procedures

All patients being considered for the study and eligible for screening must sign an informed consent for the study prior to any study-specific procedures. Subjects should be screened to determine if they are healthy enough to go back on the investigational agent. Following completion of the pretreatment assessments and confirmation of eligibility by the Lead Investigator, patients may be treated.

3.5.9.2. On-study Procedures

Patients will receive dosing of AG-013736 as outpatients. Clinic visits will be performed, and hematology, clinical chemistry and other safety laboratory tests will be done as shown in the Schedule of Tests and Procedures Table. If significant toxicity (CTC Grade \geq 3) is encountered, subsequent assessments may be performed as necessary to evaluate the specific toxicity until it resolves to baseline or CTC Grade \leq 1. Additional clinic visits may be required at the discretion of the investigator.

3.5.9.3. End of Study Procedures

The primary reason for a patient's discontinuation of the test drug will be clearly documented on the CRF. Assessments should be performed as outlined in the Schedule of Tests and Procedures Table.

Protocol: 03/21/16

End of study procedures will be performed at least 28 days after the last date of dosing or until alternative therapy is begun, whichever is sooner. A final safety assessment will be done no sooner than Day 28.

Page 20 of 53

Adverse events that are serious, suspected to be related to study drug, or considered significant by the Lead Investigator must be followed after the time of therapy discontinuation until the event or its sequelae resolve or stabilize at a level acceptable to the investigator and the Pfizer medical monitor or his/her designated representative. Each serious adverse event (SAE) must be reported to Pfizer using the contact information provided in Appendix A.

3.5.9.4. Pregnancy Follow-Up

If the participant, or their partner, become pregnant during the study or within 90 days (180 days for males) after they have stopped taking the study drug, they will be asked to inform the Lead Researcher immediately. They will also be requested to inform the doctor who will be taking care of them or their partner during the pregnancy that they or their partner took part in this study. The study doctor will ask if they, or their partner or their pregnancy doctor would be willing to provide updates on the progress of the pregnancy and its outcome. If they/their partner/their pregnancy doctor agree, this information will be provided to the study sponsor for safety monitoring follow-up.

